11	ETHICAL CONSIDERATIONS	36
12	STUDY FINANCES	36
12.1	FUNDING SOURCE	36
12.2	CONFLICT OF INTEREST	36
12.3	SUBJECT STIPENDS OR PAYMENTS	376
13	PUBLICATION PLAN	376
14	REFERENCES	38

List of Abbreviations

LIST OF ABBREVIATIONS

BP	Blood Pressure
CRTU	Clinical Research and Trials Unit
DBP	Diastolic Blood Pressure
DSMP	Data and Safety Monitoring Plan
ECG	Electrocardiography
FMD	Flow-Mediated Vasodilation
FTP	File Transfer Protocol
HIPAA	Health Insurance Portability and Accountability Act
HR	Heart Rate
IND	Investigational New Drug Application
IRB	Institutional Review Board
PHI	Protected Health Information
SBP	Systolic Blood Pressure
UPIRTSO	Unanticipated Problems Involving Risk to Subjects or Others

Study Summary

Title	Cardiovascular Effects of Adderall in Healthy Young Adults. A Randomized Clinical Trial.
Running Title	Cardiovascular Effects of Adderall in Healthy Young Adults.
Protocol Number	16-004743
Phase	Phase I
Methodology	Double blind, randomized, placebo controlled, cross-over study
Overall Study Duration	2016-2019
Subject Participation Duration	2 study day visits
Single or Multi-Site	Single-site
Objectives	To investigate the blood pressure and heart rate response to consumption of a dose of Adderall in healthy young subjects
Number of Subjects	30
Diagnosis and Main Inclusion Criteria	
 1) Adults 18 years of age and older 2) Healthy subjects without known cardiovascular disease, thyroid disease or documented mental health illness 3) Subjects who are on no medications that directly interact with the study drug 4) Subjects with no prior history of regular amphetamine use, and non-prescription stimulants 5) Nonsmokers
Study Product, Dose, Route, Regimen	Adderall 25 mg PO once
Duration of Administration	1 time dose of Adderall and 1 time dose of placebo drug
Reference therapy	Placebo drug
Statistical Methodology	Student t test will be used for between group comparisons. Data will be also analyzed using two-way analysis of variance for repeated-measures.

1 Introduction

This document is a protocol for a human research study examining the acute cardiovascular effects that may result from ingesting a dose of a common, but frequently abused, prescription medication, Adderall. Adderall will be studied in healthy young adults for whom Adderall is not clinically indicated. This study will be carried out in accordance with the applicable United States government regulations and Mayo Clinic research policies and procedures.

Attention-deficit/hyperactivity disorder (ADHD) is a disorder commonly diagnosed in school-age children. As the name implies, it is characterized by limited attention span, hyperactivity, impulsivity, an inability to concentrate, leading to poor school performance. The diagnosis of ADHD among children and adolescence increased substantially over the last 2 decades. More recently “adult” ADHD has emerged as a new diagnosis. Adderall, containing dextroamphetamine and amphetamine salts, is an approved pharmacologic therapy for ADHD and belongs to a class of prescription drugs with high potential for abuse. An estimated 10% of school-age children and adolescents suffer from ADHD and are prescribed Adderall. ADHD medication prescriptions written for children and adolescents age 3-19 years old increased by 80% from 1998 to 2005, from 6.5 million prescriptions to almost 12 million over 8 years.¹

Among the controversies associated with amphetamines, particularly Adderall, is the abuse in individuals who do not possess a prescription for the medication but who seek the stimulant effects of the drug, to improve their cognitive, academic performance or to experience euphoria. Adderall in such instances is used sporadically (i.e. Adderall-naïve individuals), sometimes in a reckless manner. The stimulating effects of amphetamines appear to be dose dependant. Young people often believe that “more is better”, leading to the intermittent but frequent consumption of high doses of Adderall, often in combination with other stimulants, smoking or alcohol. The potential adverse effects of Adderall are frequently ignored.

Nonmedical users commonly obtain the stimulant medications from their friends and peers. The abuse of prescription stimulants among young adults has brought up serious public health concerns. The number of emergency department visits due to side effects from prescription stimulants more than doubled over the last 5 years. Case reports of serious cardiac events, and even cases of sudden death have been reported.

While significant research focus has been on the neurocognitive effects of Adderall in ADHD population, little is known about its cardiovascular consequences in those not carrying the ADHD diagnosis, who take Adderall intermittently, only as a “study-drug”. The proposed research study is a randomized, double-blind, placebo-controlled clinical trial to investigate the acute cardiovascular effects of Adderall in a population of healthy, young people, in whom Adderall is not clinically indicated.

1.1 Background

Increasing number of healthy US students report nonmedical use of prescription stimulants, mainly amphetamines, such as Adderall, to improve their mental focus and academic

performance.²⁻⁵ A University of Kentucky study found that 34% of students used the drugs illegally without prescription during times of high academic stress.⁴ Students report almost immediate increase in attention span, calmer demeanor, greater emotional stability and improvement in school and academic performance.

Amphetamines act by stimulating both the central and autonomic nervous system, increasing the release of neurotransmitters dopamine and norepinephrine at the neuronal synapses, while simultaneously inhibiting their reuptake.⁶ Amphetamines were implemented as a drug to treat ADHD on this basis, suspecting that increased dopamine in the brain would amplify the capacity of children with ADHD to focus on a given task.

The unsupervised, unauthorized abuse and black market sale of Adderall has raised serious public health concerns. The increasing number of young adults who consume a variety of stimulants parallels with an increasing number of emergency department visits due to side effects.²⁻⁴ Case reports have linked prescription amphetamines with development of acute cardiac events such as myocardial infarction, coronary thrombosis, aortic dissection and sudden cardiac death.⁷⁻⁹ Reports of new tachyarrhythmias, cardiomyopathies, and systemic and pulmonary hypertension have also been reported.^{10,11} A joint study conducted by Columbia University and the New York State Psychiatric Institute (per request of the FDA) determined that the odds of sudden death in children between ages 7-19 years old were 7.4 times higher in individuals prescribed ADHD stimulants.⁷ Researchers from the University of Texas Southwestern Medical Center noted a link between amphetamine abuse and occurrence of cardiac arrest, secondary to excessive stimulant consumption, potentially inducing acute inflammatory responses and arterial vasospasms, thus reducing blood supply to the heart muscle.⁸ The mechanisms of these effects however remain unclear.

Stimulants such as amphetamines and methampethamies have been also increasing recognized to contribute to heat –related illness risk. Several case reports describing possible amphetamine related “heat stress” leading to complicated cardiovascular outcomes.¹²⁻¹⁵ Limited literature is currently available on the effects of stimulants on body’s core temperature and possible risk for stroke.

It is speculated that the adverse events are due to the high sympathomimetic action of stimulants. However, to our knowledge, the mechanisms and magnitude of such hemodynamic responses that may occur with nonmedical use of Adderall in Adderall-naïve, healthy young adults have not been studied in humans in a randomized, double-blind, placebo-controlled fashion.

The acute cardiovascular effects of stimulants in healthy young people are likely to be significant. Considering the increased use of Adderall in adults, these risks may be even higher in people with preexisting cardiac conditions (unidentified hypertension, coronary disease, silent arrhythmias) or in those with a family history of premature heart disease. The goal of the proposed clinical trial is to investigate acute cardiovascular effects of Adderall, administered orally, in healthy, young people not used to amphetamines. We hypothesize that taking an oral dose of Adderall, compared to a placebo pill, increases blood pressure (BP) and heart rate (HR) in Adderall-naïve healthy adults at rest and in response to conditions of mental and physical stress. Furthermore, we hypothesize that these hemodynamic changes are associated with sympathetic activation and

impaired endothelial and cardiac function, which could itself predispose to increased cardiovascular risk. Lastly, we hypothesize that taking an oral dose of Adderall, compared to a placebo pill, alters thermoregulation and acutely suppresses appetite in Adderall-naïve healthy adults.

1.2 Investigational Agent

-Name of investigational drug: Dextroamphetamine and amphetamine

-Brand name: Adderall

- Oral Generic Adderall: total of 25 mg dose. This dose will be compounded by CRTU Pharmacy. The compounded dose will contain: [dextroamphetamine sulfate 6.25 mg, dextroamphetamine saccharate 6.25 mg, amphetamine aspartate monohydrate 6.25 mg, amphetamine sulfate 6.25 mg (equivalent to amphetamine base 15.73 mg)].

The mean elimination half-lives for d-amphetamine and l-amphetamine in adults are 10 and 13 hours, respectively. To ensure the drug is entirely out of the subject's system, we will separate the visits by at least 5 half-lives (65 hours, approx. 3 days). To be safe we will separate study days by at least 5 days.

The duration of effect for Adderall is suggested to be somewhere between 4-6 hours, with the peak effect at 3 hours.

There will be a study run-in phase to determine appropriate dose level for study drug, but there will not be any formal interim analysis. If the drug dose is deemed inadequate, the dose will be increased to 35 mg dose.

-Pharmacologic Category: Central Nervous System Stimulant

Amphetamines are sympathomimetic amines with central nervous system stimulant activity. Amphetamines promote release of catecholamines (primarily dopamine and norepinephrine) from their storage sites in the presynaptic nerve terminals. Amphetamines also block the reuptake of catecholamines by competitive inhibition.

We will study the cardiovascular effects of generic short acting Adderall, 25 mg, as this is the dose commonly misused by young adults. This dose is also reflective of frequent adult doses used in ADHD and in narcolepsy. In general, the drug may be administered without regard to meals. Our subjects will be fasting prior to initiation of the study. Pregnancy tests will be performed prior to each study day and subjects with positive test results will be excluded for the study. Adderall is a pregnancy class C drug, meaning that the risk cannot be ruled out. Studies in animals have revealed adverse effects on the fetus (teratogenic or embryocidal effects or other), and there are no controlled studies in women, or studies in women and animals are not available. The drug will be compounded/over encapsulated by the Research Pharmacy in lactose powder for blinding purposes, and thus we will exclude subjects with known history of lactose intolerance.

According to the drug information as described in UpToDate and Lexicomp, the initial recommended oral dosing for adults with ADHD is 5 mg once or twice daily; increasing daily dose in 5 mg increments at weekly intervals until optimal response is obtained; usual maximum dose is 40 mg daily given in 1 to 3 divided doses per day. The recommended initial oral dose of Adderall for adults with narcolepsy is 10 mg daily; increasing daily dose in 10 mg increments at weekly intervals until optimal response is obtained; maximum dose: 60 mg daily given in 1 to 3 divided doses per day.

The medication does not require renal or hepatic dosage adjustments. Since we are studying healthy young subjects, we expect them to have normal renal and hepatic function.

Relevant pharmacodynamics and pharmacokinetics of Adderall are as follows:

- Duration of action: Tablet: 4 to 6 hours
- Half-life elimination: Adults: d-amphetamine: 10 hours; l-amphetamine: 13 hours
- Metabolism: Hepatic oxidation via cytochrome P450 to 4-hydroxyamphetamine (active) norephedrine (active), and alpha-hydroxy-amphetamine with both active metabolites subsequently oxidized to 4-hydroxy-norephedrine. Cytochrome P450 2D6 is primarily responsible for the formation of 4-hydroxy-amphetamine.
- Time to peak: Adderall: 3 hours.
- Excretion: Urine (highly dependent on urinary pH); excreted as unchanged amphetamine (30%, may range from ~1% in alkaline urine to ~75% in acidic urine), and derivatives of alpha-hydroxyamphetamine (50%)

Adderall is Controlled Substance, C-II. The alert US Boxed Warning states the drug's potential of abuse, stating "Amphetamines have a high potential for abuse. Administration of amphetamines for prolonged periods of time may lead to drug dependence and must be avoided. Particular attention should be paid to the possibility of persons obtaining amphetamines for nontherapeutic use or distribution to others, and the drugs should be prescribed or dispensed sparingly. Cardiovascular events: Misuse of amphetamines may cause sudden death and serious cardiovascular adverse events."

Please see the documents which are attached to the IRB application for complete information on Adderall, as provided by Lexicomp (available via UptoDate).

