- Psychiatric disorders: Use with caution in patients with preexisting psychosis or bipolar disorder (may induce mixed/manic episode). May exacerbate symptoms of behavior and thought disorder in psychotic patients; new onset psychosis or mania may occur with stimulant use; observe for symptoms of aggression and/or hostility. Screen patients with comorbid depressive symptoms prior to initiating treatment to determine if they are at risk for bipolar disorder.
- Seizure disorder: Limited information exists regarding amphetamine use in seizure disorder (Cortese, 2013). The manufacturer recommends use with caution in patients with a history of seizure disorder; may lower seizure threshold leading to new onset or breakthrough seizure activity.
- Tourette syndrome: Use with caution in patients with Tourette syndrome; stimulants may unmask tics.

To minimize the risk of side effects, we elected to use a short acting form of Adderall. Participants will be closely monitored in the CRTU at St Mary's Hospital where medical personnel is available to assist if medical needs were to arise.

2 Study Objectives

Primary Objective

- 1) Determine the hemodynamic changes (magnitude of BP and HR response) in healthy adults after taking one dose of prescription medication Adderall 25 mg orally, one time, and compare these responses to those after a placebo pill

Secondary Objective

- 1) Determine ECG changes and incidence of arrhythmias after consumption of Adderall compared to baseline ECG
- 2) Determine if consumption of a dose of Adderall is associated with altered neurohormonal and cardiovascular activation, assessed by measurements of biomarkers, such as catecholamines before and after Adderall/placebo intake
- 3) Determine if taking Adderall induces orthostatic changes
- 4) Assess baroreflex sensitivity (pace breathing) after Adderall vs placebo intake
- 5) Determine the effect of Adderall on cardiovascular hemodynamics during stress conditions including mental stress (arrhythmics), physical stress (sustained hand grip) and pain stress (cold pressor stress) as compared to measurements at rest
- 6) Determine the changes in heart function and brachial artery reactivity after Adderall intake by using an ultrasound
- 7) Determine the changes in appetite and food consumption after Adderall vs placebo

- 8) Determine the prevalence of stimulant medication use, history of weight changes and dietary habits among healthy adults (utilizing standard questionnaires)

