3.1 General Design

The cardiovascular effects of Adderall, prescription medication often abused by students for non-medical purposes, are not well understood. This is a pilot study to investigate the cardiovascular and metabolic response to taking an oral dose of Adderall (25 mg) by healthy adults. Subjects will be studied using a randomized, double-blind, placebo-controlled, crossover design with two separate experimental sessions: Adderall and placebo pill; studies will be performed on 2 separate study days, each study lasting from 6-8 hours.

[figure not shown]
Active drug: Oral Generic Adderall: total of 25 mg dose. This dose will be compounded by Pharmacy. The compounded dose will contain: [dextroamphetamine sulfate 6.25 mg, dextroamphetamine saccharate 6.25 mg, amphetamine aspartate monohydrate 6.25 mg, amphetamine sulfate 6.25 mg (equivalent to amphetamine base 15.73 mg)].

Placebo drug: Placebo designed by CRTU Research Pharmacist team

Adderall and placebo drug will be prepared by research pharmacists in similar capsule form. Placebo pill is carefully designed by our team of CRTU Research Pharmacists to match the prescription medication, Adderall. Both drugs will be given in an identical manner so that participants and study investigators are not aware of which drug is being administered. Subjects will remain unaware of the nature of the drug administered on each study day throughout the study. Each experimental session (Adderall and placebo pill) will be conducted using the same protocol, in a random order.

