11. Study personnel will perform paced breathing test, details described in the IRB Protocol. Breathing will be measured by elastic bands around the chest and abdomen.
12. Baseline endothelial function test will be performed by the study team.
13. Study personnel will perform orthostatic BP and HR measurements.
14. Study personnel blinded to the study will give the participant the study drug vs placebo drug with a glass of water, according to the randomized, double-blind, placebo-control crossover design of this study.
15. Study subject will be asked to rest in sedentary or recumbent position for 3 hours.
16. CRTU Staff will do blood draw #2 after 30 minutes of supine resting, 3 hours after intake of active drug/placebo drug.
17. The 12-lead ECG recording continues on.
18. Study personnel will perform post-intervention paced breathing test, details described in the IRB Protocol. Breathing will be measured by elastic bands around the chest and abdomen.
19. Post intervention endothelial function test will be performed by the study team.
20. Post intervention ultrasound of the heart may be performed by the study team or echo lab personnel.
21. Study personnel will perform orthostatic BP and HR measurements.

22. Study personnel will describe the series of stress tests that will follow and BP, HR, ECG measurements will continue through the stress tests.
23. Study personnel will perform series of stress tests (physical, mental, and cold stress), details described in the IRB Protocol. During the stress tests continuous BP, HR and 12-lead ECG data will be recorded and will continue to be recorded the recovery time periods.

Participants will be allowed to eat, selecting meals from a prepared menu.

24. Study subjects will be scheduled a follow up appointment in the CRTU to be done within 2 months (minimum 5 days apart) but at the same time of the day; and will be dismissed home for the day.

6.2 Visit 2

CRTU Day # 2

1. Subjects report to SMH CRTU at the already pre-scheduled appointment time. Participants should not eat at least 4 hours prior to coming to CRTU. Participant is reminded to avoid all stimulants including caffeine and alcohol 24 hours prior to the study.
2. CRTU personnel informs study personnel when the subject arrives at the CRTU.
3. Study personnel explain the research plan for day #2 and answers any questions the participant may have.

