5. Blood samples: A peripheral IV catheter will be inserted into patient's forearm to obtain blood samples and will be kept until the end of the day study. Samples will be obtained at baseline and after study drug/placebo drug administration during supine rest. About 1/2 cup of blood will be drawn with each blood draw to measure cardiovascular markers. Blood samples will be stored safely for future studies of serum markers and will be given a code.
6. Paced Breathing: This involves measurements of HR variability and baroreflex sensitivity to enable better characterization of cardiometabolic changes done before and after drug intake. Subjects will undergo detailed training to perform spontaneous and controlled breathing tests in the supine position. Continuous non-invasive blood pressure will be monitored during this test using a small finger BP cuff. Breathing will be measured by elastic bands around the chest and abdomen.
7. Stress response: The effects of study drug/placebo drug on cardiovascular/circulatory response to stress stimuli will be also studied. Stress tests (sustained handgrip, mental stress, and the cold pressor test) will be conducted in a sequential fashion and continuous BP and HR measurements will be done. Mental stress will be conducted by asking the subjects to complete serial mathematical tasks as fast as possible for three minutes. Physical stress, isometric hand grip performed with a dynamometer and by asking the subjects to sustain a handgrip of one-third of their maximum voluntary hand grip contraction maintained for 2 minutes. The cold pressor test requires subjects to place one hand into an ice water for three minutes up to the level of the wrist. The cold pressor test will be performed always last because of sustained effects of the test. Throughout all tests, measurements of BP, HR, ECG and SpO₂ will be obtained.
8. Ultrasound of the heart and arm vessel: Ultrasound assessment of heart and flow-mediated vasodilation (FMD) of the brachial artery will be performed. B-mode images and Doppler flow

will be collected to estimate brachial artery diameter and blood flow velocity. After baseline measures, reactive hyperemia will be induced by the inflation of a BP cuff placed around the forearm to a pressure of 50 mmHg above SBP (to a maximum of 200 mmHg) for 5 minutes, followed by release. Brachial artery diameter and flow velocity will be measured after deflation to measure FMD and shear stress rate.

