For this study, the study treatment follow-up period is defined as 4 hours following the last administration of study treatment. The mean elimination half-life for d-amphetamine and l-amphetamine in adults are 10 and 13 hours, respectively. We will continue to monitor the subject until the completion of study protocol each day after ingestion of the drug (anticipating for about 4 hours) in the CRTU. After this time, subjects will be instructed to present to the Emergency Department if within next 24 hours any side effects of Adderall occur. Subjects will also notify the investigators of this study of any side effects.

To ensure the drug is entirely out of the subject's system, we will separate the study visits by at least 5 half-lives (65 hours, approx. 3 days). We will lengthen this interval to be on the safe side to minimum of 5 days between the studies.

Preexisting Condition

A preexisting condition is one that is present at the start of the study. A preexisting condition should be recorded as an adverse event if the frequency, intensity, or the character of the condition worsens during the study period.

General Physical Examination Findings

At screening, any clinically significant abnormality should be recorded as a preexisting condition. At the end of the study, any new clinically significant findings/abnormalities that meet the definition of an adverse event must also be recorded and documented as an adverse event.

Post-study Adverse Event

All unresolved adverse events should be followed by the sponsor-investigator until the events are resolved, the subject is lost to follow-up, or the adverse event is otherwise explained. At the last scheduled visit, the sponsor-investigator should instruct each subject to report, to the sponsor-investigator, any subsequent event(s) that the subject, or the subject's personal physician, believes might reasonably be related to participation in this study.

Abnormal Laboratory Values

The only laboratory value we will obtain prior to initiation of the study protocol is pregnancy test. If positive, subject will be informed of the results and will be excluded from participation in the study.

Hospitalization, Prolonged Hospitalization or Surgery

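### The adverse-event period ends 4 h after dosing against a quoted effect of 4 to 6 h, with no BP/HR condition on release and no contact scheduled after visit 2

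*Combined protocol and SAP*

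**What the plan says.** On timing, section 1.2 states: "The duration of effect for Adderall is suggested to be somewhere between 4-6 hours, with the peak effect at 3 hours". Section 8.1 (Adverse Event Reporting Period) states: "the study treatment follow-up period is defined as 4 hours following the last administration of study treatment". In-unit monitoring continues "until the completion of study protocol each day after ingestion of the drug (anticipating for about 4 hours) in the CRTU". After that, subjects are told to attend the Emergency Department for side effects in the next 24 h and to inform the investigators. Section 3.1 gives the length of the whole day: "each study lasting from 6-8 hours".

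On release, BP and HR are taken every 1 to 3 minutes and recorded continuously through the stress tests and recovery (sections 6.1 and 6.2). The cold pressor test ends the series: "The cold pressor test will be performed always last because of sustained effects of the test". A meal follows. At visit 1, step 24, subjects are given the next appointment "and will be dismissed home for the day". Visit 2 ends with the meal and payment.

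On later contact, section 8.2 requires questioning about adverse events at each contact. Once the study period is over, it requires recording only of serious events that are at least possibly related.

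On dose, section 1.2 has a run-in to settle the dose level, and then: "If the drug dose is deemed inadequate, the dose will be increased to 35 mg dose". The primary objective in section 2 is the response "after taking one dose of prescription medication Adderall 25 mg orally, one time". The regimen (5.2), packaging (5.7) and toxicity statement (8) also name 25 mg only.

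**The concern.** The period in which all adverse events must be recorded can close while, on the protocol's own figures, the drug is still acting. It closes 1 h after the quoted peak. A subject whose BP or HR is still raised when procedures end can go home without any stated check against a limit. For a subject on active drug at visit 2, nobody is then due to ask what happened. Palpitations at 5 h would be non-serious and outside the period, and would be known only if the subject volunteered them.

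The stakes are subject safety and complete adverse-event counts. The primary BP and HR comparison is unaffected, because it uses measurements starting 3 h after dosing. Section 3.4 names no primary safety endpoint. However, the study is rated above minimal risk, and its subject is the acute effects of a stimulant in people not used to it. Late drug effects are therefore events it should not lose.

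**Working it through.** The plan gives no calculated figure to reproduce here. The check sets its times side by side.

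1. **Effect against follow-up.** Inputs: peak 3 h and effect 4 to 6 h (section 1.2); period 4 h (section 8.1).
   - Observed after the peak: 4 − 3 = 1 h.
   - Quoted effect remaining after the peak: 4 − 3 = 1 h to 6 − 3 = 3 h.
   - Effect outside the period: 4 − 4 = 0 h to 6 − 4 = 2 h. The period covers 100% to 4/6 = 67% of the quoted effect.

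2. **Drug level.** Inputs: half-lives 10 h (d-amphetamine) and 13 h (l-amphetamine), section 1.2. Assuming first-order decay from the 3 h peak, the fraction of peak is 0.5^((t − 3)/half-life).
   - At 4 h: 0.5^(1/10) = 93% and 0.5^(1/13) = 95%.
   - At 6 h: 0.5^(3/10) = 81% and 0.5^(3/13) = 85%.
   - This describes concentration, not effect. It shows that neither 4 h nor 6 h can be taken as the end of exposure.

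3. **When subjects leave.** Input: 6 to 8 h day (section 3.1). The pre-dose part is not given. I assume 2 h, range 1.5 to 2.5 h.
   - 6 h day: 6 − 2.5 = 3.5 h to 6 − 1.5 = 4.5 h after dosing.
   - 8 h day: 8 − 2.5 = 5.5 h to 8 − 1.5 = 6.5 h after dosing.
   - Conversely, if the 4 h anticipated in section 8.1 holds every day, the pre-dose part is 6 − 4 = 2 h to 8 − 4 = 4 h, and nobody stays to 6 h.
   - So some subjects may already be covered to 6 h, but nothing in the text secures it.

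4. **Later contact.** Inputs: 30 subjects in blocks of 6 (section 5.3), visits 5 days to 3 months apart (section 6.1; step 24 says within 2 months).
   - 30/6 = 5 blocks. With the two orders balanced 3:3 in each, 5 × 3 = 15 subjects take active drug at visit 2.
   - After visit 1, the next scheduled questioning is at visit 2. After visit 2, none is scheduled.
   - Read literally, the 4 h in section 8.1 run from the last administration, so the recording limit falls mainly on visit 2, where there is also no return visit.

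5. **Dose step.** (35 − 25)/25 = +40%. Amphetamine base rises from 15.73 mg to 15.73 × 35/25 = 22.02 mg. Against the quoted daily maxima, 35/40 = 87.5% (ADHD) and 35/60 = 58% (narcolepsy).

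**The case against.** The strongest reply is that supervision is closer than the 4 h figure suggests. Monitoring lasts until the day's procedures end, and 4 h is only anticipated. The quoted peak is observed. After the 3 h wait come a blood draw, paced breathing, the brachial artery test, orthostatic readings, three stress tests with recovery and a meal, so release at 3.5 h is implausible. The shortfall may be zero. Subjects receive the 24 h emergency advice and are asked to report side effects; unresolved events are followed to resolution. The principal investigator can end participation, and section 8.4 allows a stop for safety concerns. A Data and Safety Monitoring Plan exists (section 10.1) but is not among the documents and may say more. All of this stands, and it limits the size of the point. None of it, in the text available, extends the period, sets a release condition or schedules a contact after visit 2.

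A reader might infer three stronger things that the documents do not support:

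- That BP and HR go unchecked before release. They are measured throughout and during recovery from the stress tests; what is absent is a condition that the readings must meet.
- That the cold pressor test is shown to leave subjects unstable at dismissal. The remark about sustained effects explains the test order, and recovery and a meal come before release.
- That the dose would be raised on weak response whatever the tolerability. Section 1.2 says only that the dose is judged inadequate. A run-in to find an appropriate dose does not exclude tolerability, and the general safety stop applies at any dose.

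**Conclusion.** The point holds as a cheap improvement to safety and adverse-event capture. The stated period leaves 0 to 2 h of the protocol's own effect window uncovered. Release carries no BP or HR condition. For about 15 of 30 subjects, active drug is followed by no scheduled contact. The 0 to 2 h uses the protocol's own times; the 15 assumes that 30 subjects are enrolled and that each block balances the two orders. How many subjects now leave before 6 h cannot be determined from the documents.

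The dose step is secondary and minor. The 40% increase has no stated criterion and no tolerability condition, but it may never be taken, and 35 mg lies below both quoted daily maxima. On its own it would be missing detail.

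**What to change.** In section 8.1, run the adverse-event period to 24 h after each dose, which matches the existing emergency advice, and add a short call at 24 h after both visits.

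In sections 6.1, 6.2 and 8, release subjects no earlier than 6 h after dosing. Before release, the investigator reviews the resting BP and HR readings already being taken, after recovery from the cold pressor test, against limits that the investigator sets in advance. The documents supply no basis for particular numbers. Step 2 of the working suggests that a strict return to pre-dose values by 6 h may often not be met on active drug. The rule must be identical at both visits so that the blind holds.

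In section 1.2, if the 35 mg option is kept, state what counts as inadequate, who decides, and that the step is not taken when run-in tolerability at 25 mg is poor. Deleting the option is also possible, but gives up a higher dose should 25 mg prove too low.

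The cost is 0 to about 2 h more per visit for some subjects. If every subject would otherwise leave at 4 h, this is 30 × 2 visits × 2 h = 120 unit hours. It is more where the review delays release beyond 6 h. The calls number 30 × 2 = 60. The dose wording costs nothing to add.
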